### Taper Period

Subjects who complete the study or who discontinue early will return for an End of Study (EOS) Visit or Early Discontinuation Visit (EDV), respectively, and will be progressively tapered off over 4 weeks and return to the site 1 week after the last PSL intake for an end of Taper Visit.

### Safety Follow-up Period

---

Safety follow-up will consist of 1 required visit (SFU Visit) 30 days after the last PSL intake. A follow up echocardiogram will be required at approximately 1 month and 6 months after the last PSL intake.

Subjects must return to the clinic for scheduled visits as outlined in [Table 2-1](#).

This document cannot be used to support any marketing authorization application and any extensions or variations thereof.

REDACTED COPY

**Table 2-1: Schedule of assessments**

	Setting (Required Onsite s )	Entry Visit	Evaluation Period a							EOS Visit	EDV Visit	Taper Period (including 1 Wk drug free)	SFU (30 days after last PSL intake)	Unsch Visit/TC	
			Bi-weekly Visits		Monthly Visits		Visits every 3 M		EOS c						EDV c
			V1 b	V2	V3	V4	V5	V6, V8, V10							
Assessments		Wk 0	Wk 2	Wk 4	M2	M3	M6, M12, M18	M9, M15, M21	M24		Up to 4 Wk				
Written informed consent	NA – V1 as per UCB requirement had to be performed onsite	X													
Dispensation of Subject Trial card	NA – V1 as per UCB requirement had to be performed onsite	X													

**Table 2-1: Schedule of assessments**

	Setting (Required Onsite s )	Entry Visit	Evaluation Period a							EOS Visit	EDV Visit	Taper Period (including 1 Wk drug free)	SFU (30 days after last PSL intake)	Unsch Visit/TC	
			Bi-weekly Visits		Monthly Visits		Visits every 3 M		EOS c						EDV c
			V1 b	V2	V3	V4	V5	V6, V8, V10							
Assessments		Wk 0	Wk 2	Wk 4	M2	M3	M6, M12, M18	M9, M15, M21	M24		Up to 4 Wk				
Demographic data	NA – V1 as per UCB requirement had to be performed onsite	X													
Verification of inclusion/exclusion criteria	NA – V1 as per UCB requirement had to be performed onsite	X													
Verification of withdrawal criteria	Partially required onsite		X	X	X	X	X	X		X					

**Table 2-1: Schedule of assessments**

	Setting (Required Onsite s )	Evaluation Period a									Taper Period (including 1 Wk drug free)	SFU (30 days after last PSL intake)	Unsch Visit/TC
		Entry Visit	Bi-weekly Visits		Monthly Visits		Visits every 3 M		EOS Visit	EDV Visit	End of Taper Visit	SFU Visit	
		V1 b	V2	V3	V4	V5	V6, V8, V10	V7, V9, V11	EOS c	EDV c			
Assessments		Wk 0	Wk 2	Wk 4	M2	M3	M6, M12, M18	M9, M15, M21	M24		Up to 4 Wk		
Medical history update	NA – V1 as per UCB requirement had to be performed onsite	X											
C-SSRS since last visit d	no	X*	X	X	X	X	X	X	X	X	X	X	
HADS d	no	X			X		X	X	X	X			
SSG	no	X				X	X	X	X	X			
QOLIE-31-P d	no						X		X	X			
CIWA-B d	no								X e	X	X	X	
TSQM-9 d	no								X	X			
Vital signs f	yes	X*	X	X	X	X	X	X	X	X	X	X	
Body weight	no	X*		X		X	X	X	X	X		X	

**Table 2-1: Schedule of assessments**

	Setting (Required Onsite s )	Evaluation Period a								Taper Period (including 1 Wk drug free)	SFU (30 days after last PSL intake)	Unsch Visit/TC	
		Entry Visit	Bi-weekly Visits		Monthly Visits		Visits every 3 M		EOS Visit	EDV Visit	End of Taper Visit		SFU Visit
		V1 b	V2	V3	V4	V5	V6, V8, V10	V7, V9, V11	EOS c	EDV c			
Assessments		Wk 0	Wk 2	Wk 4	M2	M3	M6, M12, M18	M9, M15, M21	M24		Up to 4 Wk		
Physical examination g (XF = Full – XB = Brief)	yes	XF*		XB		XB	XB	XB	XB	XB	XB	XB	
Neurological examination h (XF = Full – XB = Brief)	yes	XF*		XB		XB	XB	XB	XB	XB	XB	XB	
Psychiatric and Mental Status	no	X*		X		X	X	X	X	X	X	X	
Personal Outcomes assessment l	yes						X	X					
12-lead ECG j	yes	X*		X		X		X	X	X		X	
Echocardiogram k	yes		X			X	X	X	X k			X	
Blood/urine sample for clinical laboratory analysis	yes	X*		X	X	X	X	X	X	X			

**Table 2-1: Schedule of assessments**

	Setting (Required Onsite s )	Evaluation Period a									Taper Period (including 1 Wk drug free)	SFU (30 days after last PSL intake)	Unsch Visit/TC
		Entry Visit	Bi-weekly Visits		Monthly Visits		Visits every 3 M		EOS Visit	EDV Visit	End of Taper Visit	SFU Visit	
		V1 b	V2	V3	V4	V5	V6, V8, V10	V7, V9, V11	EOS c	EDV c			
Assessments		Wk 0	Wk 2	Wk 4	M2	M3	M6, M12, M18	M9, M15, M21	M24		Up to 4 Wk		
Pregnancy test (female subjects only) l	yes	X*	X	X	X	X	X	X	X	X	X	X	
Seizure evaluation (count and type) m	no	X*	X	X	X	X	X	X	X	X	X	X	
Concomitant medications and procedures n	no	X*	X	X	X	X	X	X	X	X	X	X	
Recording of adverse events	no	X*	X	X	X	X	X	X	X	X	X	X	
Health-related outcomes and HRU	no	X*	X	X	X	X	X	X	X	X	X	X	
IRT call	no	X										X	
PSL dispensing (IRT)	no	X	X	X	X	X	X	X	X p	X			
PSL accountability and return o	no		X	X	X	X	X	X	X	X	X		

**Table 2-1: Schedule of assessments**

	Setting (Required Onsite s )	Evaluation Period a								Taper Period (including 1 Wk drug free)	SFU (30 days after last PSL intake)	Unsch Visit/TC	
		Entry Visit	Bi-weekly Visits		Monthly Visits		Visits every 3 M		EOS Visit				EDV Visit
		V1 b	V2	V3	V4	V5	V6, V8, V10	V7, V9, V11	EOS c				EDV c
Assessments		Wk 0	Wk 2	Wk 4	M2	M3	M6, M12, M18	M9, M15, M21	M24		Up to 4 Wk		
Study termination	NA – this is not an assessment								X q		X r		

AED=antiepileptic drug; BP=blood pressure; CIWA-B=Clinical Institute Withdrawal Assessment-Benzodiazepines; C-SSRS=Columbia-Suicide Severity Rating Scale; ECG=electrocardiogram; EDV=Early Discontinuation Visit; EOS=End of Study; HADS=Hospital Anxiety and Depression Scale; HRU=healthcare resource utilization; IRT=interactive response technology; M=month; PSL=padsevonil; QOLIE-31-P=Quality of Life Inventory in Epilepsy-31-P; SFU=Safety Follow-up; SSG=Seizure Severity Global Item; TC=telephone call; TSQM=Treatment Satisfaction Questionnaire for Medication; Unsch=unscheduled; V=visit; Wk=week, NA=Not Applicable

a At any point during the Evaluation Period, an unscheduled visit may be conducted due to safety or efficacy reasons. Appropriate assessments will be conducted in relation to the reason for the visit. If an unscheduled visit is conducted due to safety or efficacy reasons, a C-SSRS assessment will be performed with the subject during the visit. If an unscheduled visit is conducted for reasons other than safety or efficacy concerns (eg, replacement of lost medication, repeated collection of a laboratory specimen due to collection or analysis issues), a C-SSRS will not be required at these visits.

b Entry Visit (Visit 1) will be done on the same day as the last visit of parent study. Data from parent study will be used (identified by \*) and corresponding assessments will not be repeated.

c The Taper Period is only valid for subjects discontinuing the study or completing without continuation of the PSL treatment. This period will last for 3 weeks plus a 1-week drug-free period.

d Questionnaires to be completed by all subjects prior to any other study procedures at the visit, when possible.

e Assessment is only valid for subjects discontinuing PSL treatment.

f Vital signs measured in supine position after 5 minutes of rest include pulse rate, respiratory rate, systolic BP, and diastolic BP.

- g Full physical examination will include assessment of cardiac and respiratory function via auscultation and review of the following body systems: general appearance; ear, nose, and throat; eyes; hair and skin; respiratory; cardiovascular; gastrointestinal; musculoskeletal; hepatic; neurological; and mental status. Brief physical examinations will include a review of the following body systems: general appearance (including mental status); skin; respiratory; cardiovascular; gastrointestinal; and hepatic.
- h Brief neurological examination will include a general assessment and evaluation of reflexes, muscle strength and coordination and cerebellar function. Full neurological examination will include in addition, evaluation of cranial nerves, motor system (general muscle strength and tone), and sensations in upper/lower extremities.
- i Personal outcome assessments will be completed at Visit 6 (Month 6) and Visit 11 (Month 21) (for subjects who agree to participate).
- j An ECG at the SFU will be performed only if abnormal at the EOS or EDV Visit. All ECG recordings will be performed with the subject resting in supine position for at least 5 minutes.
- k Only subjects who do not require tapering of PSL at M24 will have an echocardiogram at M24. All other subjects will have an echocardiogram at the SFU Visit and at 6 months after the last dose of PSL. A repeat echocardiogram will be performed for subjects with a new finding, Grade 2 severity (moderate), or Grade 3 severity (severe).
- l Results of a serum pregnancy test performed during parent study will be used at Visit 1 together with a urine test performed at Visit 1. Urine pregnancy tests will be used at all other visits for female subjects of childbearing potential.
- m Seizure counts are collected on the subject's daily record card on a daily basis.
- n Assessment includes AED history.
- o Medication should be presented at each visit for check on compliance.
- p PSL will be dispensed at the EOS Visit only to subjects who will be tapered off PSL.
- q The study termination assessment at the EOS visit is for subjects who will transfer into either a Managed Access Program or another PSL study.
- r The study termination assessment at the SFU Visit is for subjects who withdraw early or who complete the study, but will not be transferred to either a Managed Access Program or another PSL study.

**Error! Reference source not found.** Data may be collected through phone or video calls for visits that do not require onsite assessment because of COVID-19 pandemic.

## 2.4 Determination of sample size

For this OLE study, no sample size calculation is needed. The sample size will depend upon recruitment into and completion of a PSL parent studies (eg, EP0091 or subsequent PSL studies). Approximately 1000 subjects with focal-onset seizures and drug resistant epilepsy may be included.

## 3 DATA ANALYSIS CONSIDERATIONS

### 3.1 General presentation of summaries and analyses

Statistical analysis and generation of tables, figures, subject data listings, and statistical output will be performed using SAS Version 9.3 or higher. All tables and listings will use Courier New font size 9.

Decimal places for descriptive statistics will always apply the following rules:

- “n” will be an integer
- Mean, SD, and median will use one additional decimal place compared to the original data
- Minimum and maximum will have the same number of decimal places as the original value.

Derived variables in general will display the mean, SD and median to 1 more decimal place than the variables used in the derivation. If the number of decimal places reported in the raw data is varied then use either the maximum raw number of reported decimal places or 3, whichever is the lowest, as a guide for the descriptive statistics.

A complete set of data listings containing all documented data as well as calculated data (e.g., change from Baseline), as applicable, will be generated.

The total daily dose (mg/day) is presented in EP0093.

Unless otherwise stated, safety and efficacy summaries will be presented for all subjects. Selected summaries will also be presented by region.

In general, all data collected in the EP0093 clinical database and parent study data included in the analyses will be presented in the subject listings.

### 3.2 General study level definitions

#### 3.2.1 Initial processing of diary data for seizure frequency

Subjects are instructed to record in their diary all types of seizures that occur, after each seizure or at least once a day. The investigator will assess and confirm the seizures according to the ILAE codes (ILAE Classification of Epileptic Seizures, 1981) and record the seizure types and frequency in the electronic Case Report form (eCRF)/diary. Each seizure code in the clinical database will be mapped to exactly 1 of the following ILAE classification codes: I, IA, IA1, IA2,

IA3, IA4, IB, IB1, IB2, IC, II, IIA, IIB, IIC, IID, IIE, IIF, or III. With regard to cluster seizures, investigators are to report the number of cluster episodes rather than reporting the estimated number of individual seizures.

### **3.2.2 Analysis time points**

#### **3.2.2.1 First and last dose of PSL**

Unless otherwise noted, all references to the first dose of PSL in this SAP refer to the first dose of PSL during EP0093 (i.e. not the first dose of PSL from the parent studies in which subjects participated in prior to EP0093).

At the time of a clinical cutoff, for subjects who are ongoing and don't have the End of Taper Visit, the last dose of PSL will be set to the date of the clinical cutoff for the interim analyses. For subjects who are ongoing but had the End of Taper Visit at the time of a clinical cutoff, the last dose of PSL will be set to the last dosing date on the Study Medication Administration eCRF for the interim analyses.

#### **3.2.2.2 Relative day**

Relative days for an event or measurement occurring before the date of first dose of PSL in EP0093 will have a '-' prefix and will be calculated as follows:

Relative Day = -[(Event date - Date of first dose)]

Relative days for an event or measurement occurring on or after the date of first dose of PSL but not after the date of last dose of PSL in EP0093 will be calculated as follows:

- Relative Day = (Event date - Date of first dose) + 1

For events or measurements occurring after the date of last dose of PSL in EP0093, relative day in this case will be prefixed with '+' in the data listings and will be calculated as follows:

- Relative Day = + (Event date - Date of last dose)

All study level variables should be defined in subsections below. This includes analysis time points and definitions of study periods to be analyzed.

#### **3.2.2.3 Study Entry visit**

#### **3.2.2.4 The Entry Visit (EV, Visit 1) will be done on the same day as the last visit of the parent study. End date of the Evaluation Period**

The end date of the Evaluation Period will be either EOS at Month 24 or EDV for subjects who discontinue early. If a subject does not have an EOS or EDV Visit, then the final contact date will define the end date of the Evaluation Period. At the time of a clinical cutoff prior to the study completion, if a subject is ongoing and doesn't have the EDV, the end of the Evaluation Period is set to the clinical cutoff date.

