**Table 3–3.21: Start and end of EP0093 analysis periods**

Description	Start	End	Details
Evaluation Period	Entry Visit (EV, Visit 1)	EOS or EDV or the last contact date if neither EOS or EDV visit is available.  At the time of a clinical cutoff prior to the study completion, if a subject is ongoing and doesn't have the EDV, the end of the period is set to the clinical cutoff date.	The Entry Visit (EV, Visit 1) will be done on the same day as the last visit of the parent study. Subjects will return to clinic every 2 weeks during Month 1, every month during Month 2-3, every 3 months after Month 3 up to Month 24.
Taper Period/ Safety Follow-Up Period	1 day after end date of evaluation period.	The date of final contact.  At the time of a clinical cutoff prior to the study completion, if a subject is ongoing, the end of the period is set to the clinical cutoff date.	Applies only to patients who discontinue the study or complete it without continuation of PSL treatment.
Exposure Period	Date of first dose of PSL	Date of last dose of PSL	Extends from the date of first dose until the last dose of PSL in EP0093. It may include the Evaluation and Taper Period. (Section 3.2.2.1).

At the time of a clinical cutoff prior to the study completion, subjects without the Study Termination eCRF will be classified as “ongoing.” Only the data on or prior to the clinical cutoff date will be included in the analyses.

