### 3.2.5 Interval duration

A month is defined as 30 days and time intervals based on monthly durations are defined as a multiple of 30 days (eg, 12 months is defined as 360 days).

Interval Duration Definition:

- Months 0-3 Days 1-90
- Months >3-6 Days 91-180
- Months >6-9 Days 181-270
- Months >9-12 Days 271-360

Subsequent intervals are defined in a similar manner. For the analysis of seizure data during the Evaluation Period, 3-month intervals will be derived for the Evaluation Period. For the analysis of AEs and safety variables, 3-month intervals will be derived for the Exposure Period.

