### 4.1 Handling of dropouts or missing data

#### 4.1.1 Handling of missing data in seizure frequency

Seizure frequency will be calculated over non missing diary days during an analysis period or time interval. Days with missing seizure diary (ie, "Not Done" is ticked on the Seizure Count CRF) will not be considered in the calculation of seizure frequency or seizure free days. No imputation will be applied to missing seizure diary data. Seizure frequency during a time interval will be calculated if seizure data are available for at least 1 day during the interval.

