### 9.1 Extent of exposure

The overall duration of exposure of the study will be calculated as the date of last dose of PSL minus the date of first dose of PSL (Section 3.2.2.1) in EP0093 plus 1 day.

Modal daily dose of a subject will be calculated as the daily dose the subject received for the longest duration during EP0093. In the event of a tie, the modal dose will be set to the lower of the tied doses. Modal daily dose will be categorized as  $\leq 200$ mg/day,  $> 200$ mg/day to  $\leq 400$ mg/day,  $> 400$ mg/day to  $\leq 600$ mg/day, and  $> 600$ mg/day.

The duration of exposure will be summarized overall and by modal dose for the SS and by region:

- Cumulative months of exposure: duration of exposure in days will be summarized. Duration of exposure will also be categorized into the following cumulative months categories of exposure:  $\geq 3$  months,  $\geq 6$  months,  $\geq 9$  months,  $\geq 12$  months,  $\geq 18$  months, and  $\geq 24$  months.

Listings will include the study medication exposure per subject and the administration of study medication per dispense interval. Data collected on the Prescribed Padsevonil Dose CRF will be listed.

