### 10.1 Statistical analysis of the primary efficacy variables

#### 10.1.1 Derivations of primary efficacy variable

Seizure frequency (SF) refers to the 28-day adjusted seizure frequency, which is defined as:

$$SF = (\text{Number of Seizures}) \times (28 / D)$$

- where Number of Seizures = total number of seizures during an analysis period or time interval. For cluster seizures, the number of cluster episodes will be included.
- D = number of days for which the diary was available during the analysis period or time interval.

Change from Baseline in seizure frequency will be calculated as seizure frequency during an analysis period or time interval minus the Baseline seizure frequency.

The primary efficacy variable is the change from Baseline in the observable focal-onset seizure frequency over the Evaluation Period.

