### 10.2.2.11 Time to Discontinuation to Treatment

Kaplan-Meier estimates of the percentage of subjects completing 3, 6, 12, 18, and 24 months of treatment will be provided for the SS. For subjects who discontinued from the study, the event date is set to the date of last dose of PSL and the time to event will be calculated as the date of

last dose minus the date of first dose of PSL in EP0093 plus 1. Subjects who completed the study will be censored as of the date of last dose of PSL in EP0093. At a clinical cutoff, subjects who are ongoing will be censored as of the date of last dose of PSL defined for the interim analyses (Section 3.2.2.1).

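### When EOS and EDV are both missing, the Evaluation Period runs to final contact; if that falls after the last PSL dose, off-drug diary days enter the primary efficacy variable and completer-cohort duration is lengthened

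*SAP*

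**What the plan says.** SAP 3.2.2.4 ends the Evaluation Period at EOS or EDV and adds: "If a subject does not have an EOS or EDV Visit, then the final contact date will define the end date of the Evaluation Period". The analysis-period table in SAP 3.2.3 agrees: "EOS or EDV or the last contact date if neither EOS or EDV visit is available". In the same table the Taper/Safety Follow-up Period starts "1 day after end date of evaluation period" and closes at final contact.

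The period dates decide where seizure data go (SAP 3.2.3). SAP 10.1.1 takes the primary efficacy variable over the Evaluation Period, with this denominator: "D = number of days for which the diary was available during the analysis period or time interval". SAP 3.2.5 adds: "For the analysis of seizure data during the Evaluation Period, 3-month intervals will be derived for the Evaluation Period". SAP 4.1.1 sets a low threshold for an interval value: "Seizure frequency during a time interval will be calculated if seizure data are available for at least 1 day during the interval". Completer cohorts in SAP 3.2.6 use the length of the same period, counted from the Entry Visit.

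The SAP does define an Exposure Period that closes at the last dose, but SAP 3.2.5 assigns it to adverse events and safety variables. No seizure rule refers to it.

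**The concern.** A subject who has an EDV at or before the last dose has all later days assigned to Taper/Safety Follow-up. A subject who skips the EDV and is contacted after the last dose has those later days assigned to the Evaluation Period. Whether an off-drug day counts towards efficacy can therefore depend on whether a visit was attended.

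Such days can carry data. Protocol 8.3.1 places the end of diary recording at the Safety Follow-up Visit, 30 days (± 1 week) after the last intake. SAP 3.2.3.1 asks for an effort to recover all diary records of subjects who withdraw between visits, without separating on-drug from post-dose days.

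At stake are the subject's change from Baseline, responder status at the 50%, 75% and 90% cut-offs, and membership of the completer cohorts in which the seizure summaries are repeated.

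**Working it through.** The plan states no figure on this point, so there is none to reproduce. The check applies the SAP's own formulas with the period ending at final contact and then at the last dose.

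**Inputs from the documents.** Seizure frequency = seizures × 28 / D (SAP 10.1.1). Percent reduction is relative to Baseline (SAP 10.2.1.1). Duration = end of Evaluation Period − Entry Visit + 1 (SAP 3.2.6). Cohort limits are 90, 180, 360, 540 and 720 days. The Safety Follow-up Visit falls 23 to 37 days after the last dose.

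**Assumptions.** Entry Visit = first dose = Day 1; diaries complete to final contact; on-drug rate 0.6 of Baseline (a 40% reduction). S is the day of last dose, A the number of post-dose diary days, and r the post-dose rate divided by the Baseline rate. The documents give no value for r, so a range is shown.

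**1. Percent reduction.** Reported reduction = 1 − (0.6 S + r A)/(S + A).

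| r, with A = 30 | S = 60 | S = 180 |
|---|---|---|
| 0.6 (on-drug rate) | 1 − 54/90 = 40.0% | 1 − 126/210 = 40.0% |
| 0.8 | 1 − 60/90 = 33.3% | 1 − 132/210 = 37.1% |
| 1.0 (Baseline rate) | 1 − 66/90 = 26.7% | 1 − 138/210 = 34.3% |
| 1.5 | 1 − 81/90 = 10.0% | 1 − 153/210 = 27.1% |

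Across the follow-up window at r = 1 and S = 60: A = 23 gives 1 − 59/83 = 28.9%; A = 37 gives 1 − 73/97 = 24.7%. With the period ended at the last dose, every case returns 40%.

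**2. Responder status.** Take Baseline 10 per 28 days, 5 on drug for 60 days, and 10 off drug for 30 days. The reported frequency is (60 × 5 + 30 × 10)/90 = 6.67, a change of −3.33 instead of −5.00. The reduction is 33.3% instead of 50.0%, and 50% responder status is lost.

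**3. An interval with no treated day.** Last dose Day 80, diaries to contact on Day 110. The Months >3-6 interval starts on Day 91, so it gets a value from Days 91-110: 20 diary days, none on drug.

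**4. Cohort duration, with no diary data needed.** Last dose Day 60, contact Day 90: 90 − 1 + 1 = 90 days, so the subject enters the ≥3-month cohort. Ended at the last dose, the duration is 60 days.

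**5. Taper/Safety Follow-up.** For the subject in step 4 this period starts on Day 91 and ends on Day 90, so it is empty and cannot take up Days 61-90.

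**The case against.** The trigger is narrow. Protocol 8.1.7 expects an EDV from every early discontinuer. The primary variable moves only if the subject skips it, is contacted after the last dose and supplies diaries for that time. A subject lost while on drug is unaffected, and without post-dose diaries D does not grow. All of this stands and limits the size of the problem.

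A reader might infer that the rule is wrong because it contradicts the treatment clocks. For time to discontinuation, SAP 10.2.2.11 says: "For subjects who discontinued from the study, the event date is set to the date of last dose of PSL". For exposure, SAP 9.1 says: "The overall duration of exposure of the study will be calculated as the date of last dose of PSL" and subtracts the first-dose date. The documents do not support that inference. Those rules measure time on treatment, whereas SAP 3.2.6 measures the length of a study period. They also differ on the ordinary pathway: with an EDV on Day 75 and the three weeks of taper given in the schedule-of-assessments footnote, the last dose falls on Day 96, while cohort duration is 75 days. The difference is not in itself the error.

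A reader might also count the stopping days that cross a cohort limit (5 limits × 30 days = 150 of 720, or 20.8%) and take that as a share of subjects. It is a count of calendar days. Reading it as a share would need stopping to be spread evenly over two years, which the documents do not say; SAP 3.9 also records early termination of the study.

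Finally, off-drug days are not unique to the fallback. A subject who stops PSL before a late EDV also has them, for example under the liver-injury rules in Protocol 6.3.1, where withdrawal from the study waits until monitoring is complete. Today a Day-60 stopper with an EDV on Day 90 and one last contacted on Day 90 get the same period. A cap on the fallback alone would separate them. This objection is right, and it decides the form of the fix.

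**Conclusion.** The point holds as a defect in the period definition. As written, the fallback places off-drug diary days in the primary efficacy variable and the 3-month seizure-frequency and responder summaries. It can also produce an interval value with no treated day, lengthen cohort duration and empty the Taper/Safety Follow-up Period. Per affected subject the distortion runs from none to large: a 40% reduction on drug reads as 40% to 10.0% for a Day-60 stopper, and as 40% to 27.1% for a Day-180 stopper. Those figures rest on the assumed on-drug effect, the assumed post-dose rates and 30 complete post-dose diary days. The cohort and empty-period results need only a contact after the last dose.

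The overall effect cannot be sized, because the documents do not say how many subjects lack both visits. Efficacy is a secondary objective and SAP 10.1.2 plans no testing or modelling, so no error rate is involved. Safety intervals use the Exposure Period and are untouched. Seizure-free status has its own guard in SAP 10.2.1.3 (interval completed, at most 10% of days missing). The rule should not be read as flattering the drug: if seizures rise off drug, it understates benefit. The change is worth making because it is cheap, not because the study's conclusions are shown to depend on it.

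**What to change.** In SAP 3.2.2.4 and the analysis-period table, end the Evaluation Period at the earlier of (a) EOS or EDV, or final contact if neither exists, and (b) the date of last PSL dose; use (a) alone if the last-dose date is unknown. Apply this to all subjects, so that late-EDV and no-EDV subjects are handled alike. Use the same end date for the 3-month intervals and the completer cohorts, start Taper/Safety Follow-up the next day, and leave the clinical-cutoff rule unchanged. Report how many subjects used the fallback and how many were capped.

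In the examples, the Day-60 stopper returns to 40% and 60 days, with Days 61-90 in Taper/Safety Follow-up, whether Day 90 was an EDV or a last contact. The Day-80 stopper has no Months >3-6 value.

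The cost is a short change to the SAP text and table, plus the two counts. No new data are needed: SAP 5.1 lists last administration and final contact as separate Study Termination CRF variables. One downside remains: for subjects without an EDV, any taper days before the last dose stay in the Evaluation Period.
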